Aim 2: Evaluate the effect of dLPFC iTBS on cognitive performance in the presence of an alcohol cue. Following the alcohol cue reactivity task all individuals will perform the well-known alcohol Stroop task (downloaded from the NIH toolbox) on a Tablet PC while a glass of the participant’s preferred alcoholic beverage (beer, wine, liquor) is placed within 5 feet of the participant (but out of arms length). This will occur before and after TBS. The participant will not be allowed to consume the drink. Hypothesis: Stroop accuracy and reaction time will be impaired at baseline, but this difference will be attenuated by real (but not sham) iTBS to the dLPFC (three way mixed model ANOVA, correcting for multiple comparisons).

Methods and Measures

Design

Our primary goal is to determine the extent to which one session of dLPFC iTBS can attenuate limbic circuitry involved in alcohol cue-reactivity (Aim 1) and cognitive control in the presence of an alcohol cue (Aim 2) among heavy alcohol users with a history of risky drinking behavior. This will be tested in a cohort of 48 heavy alcohol users, recruited through the resources of the Wake Forest Trauma Unit Registry and from the community at large through advertisements. This double-blind, sham-controlled study will involve 1 Screening visit and 1 TBS/MRI Scanning Visits. At the scanning/stimulation visit, functional MRI data will be collected before and after exposure to a session of real or sham theta burst stimulation (Figure 1). TBS will be applied over the left dorsolateral prefrontal cortex (landmark based on EEG 10-20 system: F3). A series of clinical assessments of drinking behavior and other relevant psychosocial and demographic measurements will also be collected (Table 1). We will test the hypotheses that TBS over the dLPFC will attenuate the neural response to alcohol cues (Aim 1) and improve cognitive performance in the presence of an alcoholic beverage cue (Aim 2). The results of these aims will be further evaluated in terms of their relationship to alcohol drinking severity and demographic factors. These data will be preliminary data for a subsequent R01 focused on the sustained effects

of multiple sessions of TBS as a tool to decrease drinking among individuals with AUD and lowering morbidity and hospital recidivism among these patients.

Setting

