Cognitive Interference in the presence of an alcoholic beverage cue task: An abnormally high attentional biases towards alcohol-associated cues have been observed in alcohol-dependent patients and is related to poor treatment outcomes (review: Field & Cox 2008). This bias towards alcohol cues impairs an individual's ability to withhold responding for alcohol, narrows their behavioral repertoire, and slows performance on cognitive tasks. One of the most well-established tasks for measuring cognitive performance and interference is the Stroop Color-Word Naming Task. During the Stroop task, 100 words will be presented are presented on a computer screen in a serial manner. Participants are asked to name the color of each word presented while ignoring the meaning of the word itself. Error rates and reaction times are the primary dependent measures. Previous studies have shown that heavy alcohol users

drinkers respond more slowly after exposure to alcohol-related priming conditions (Cox et al 1999, Cox et al 2003). Consequently, after the fMRI alcohol cue reactivity task and before the Stroop task, a glass of the participant's preferred alcoholic beverage (beer, wine, liquor) will be placed within 5 feet (but out of arm's length) of the participant. It will remain there for the length of the task, but the participants will not be allowed to drink it and the beverage will be discarded at the end of the study visit. This paradigm will be repeated before and after iTBS.

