The debit card system is administered by an outside company in conjunction with the Wake Forest Office of Clinical Research (OCR) who will distribute the cards in sealed envelopes to study staff prior to a participant's screening visit. The company, Greenphire, will be given the participant's name and social security number. They will use this information only as part of the payment system. The information will not be used for any other purposes and will not be given or sold to any other company. Greenphire will not receive any information about the participant's health status or the study in which they are participating.

Outcome Measure(s)/Analytical Plan

Cognitive Interference in the presence of an alcohol beverage cue task: It is hypothesized that individuals will have slower color-naming responses for alcohol words compared to neutral words at baseline, but this effect size will be lower following real versus sham iTBS (mixed model analysis of variance, error rate and reaction time, before and after TBS, 2 groups: real iTBS and sham iTBS).

Neuroimaging Preprocessing: MRI data will be preprocessed using SPM12 (Wellcome Department of Cognitive Neurology, London, UK) implemented in Matlab 7.14 (MathWorks, Inc., Natick, MA). MR Images will be first converted from DICOM format to 4D NIfTI files and motion corrected (Realign: 6 parameter rigid-body realignment to first image in each timeseries using a least-squares approach). Normalization parameters, bias correction and anatomical tissue maps will be determined simultaneously, using the Segment toolbox. Individual anatomical images will be stripped of their skulls by masking the bias-corrected image with the combined tissue masks of grey matter, white matter, and CSF. The functional images derived from realignment will be coregistered, through the mean image, to the skull-stripped anatomical image (Coregister: Estimate, using normalized mutual information). Coregistered images will be then normalized (Normalize: Write) to MNI template space with the nonlinear warps derived from the Segment tool. Finally, functional images will be masked (to remove the skull) and smoothed (8mm FWHM Gaussian kernel) to facilitate subsequent between-subject analysis.

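### Aim 2's Stroop task is named inconsistently, and the listed measures and model do not test the stated hypothesis about alcohol versus neutral words

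*Combined protocol and SAP*

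**What the plan says.** Three places describe the Aim 2 task.

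- **Objectives, Aim 2.** Participants will "perform the well-known alcohol Stroop task (downloaded from the NIH toolbox) on a Tablet PC". The hypothesis is that "Stroop accuracy and reaction time will be impaired at baseline, but this difference will be attenuated by real (but not sham) iTBS". The test is a "three way mixed model ANOVA, correcting for multiple comparisons". The three factors are not named, and the text does not say what the baseline difference is measured against.
- **Interventions and Interactions, Cognitive Interference task.** This is the only procedural description. It introduces the instrument with "One of the most well-established tasks for measuring cognitive performance and interference is the Stroop Color-Word Naming Task". On stimuli it says "During the Stroop task, 100 words will be presented are presented on a computer screen in a serial manner", without saying which kinds of word. On outcomes it says "Error rates and reaction times are the primary dependent measures". The alcohol cue here is a glass of the preferred drink, set out at both the pre- and post-stimulation tests.
- **Outcome Measure(s)/Analytical Plan, Cognitive Interference task.** The hypothesis is that "individuals will have slower color-naming responses for alcohol words compared to neutral words at baseline", with this effect smaller after real than after sham stimulation. The model listed is a mixed-model analysis of variance on error rate and reaction time, with pre/post and the two groups as its only factors.

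**The concern.** The hypothesis in the Analytical Plan is a contrast within each participant: alcohol words against neutral words. Testing it needs a list with both classes and a model term that carries the contrast. The procedural section does not provide the first, and the listed model does not contain the second.

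Two consequences follow. First, a group x time test on plain reaction time responds to anything that changes speed in general, such as arousal after stimulation. A participant who becomes equally faster on every word has not become less distracted by alcohol words, yet would count towards a favourable result. Second, if staff took the procedural section at its word and loaded a standard colour-word list, no later analysis could recover the alcohol-word contrast. The glass of drink cannot replace it, because it is present at both tests and no drink-free condition is described.

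Aim 2 is one of the study's two aims, and its results are meant as preliminary data for a larger grant application. Choosing the score after the data are in could decide what Aim 2 is said to have shown.

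**Working it through.** **1. Side by side**

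| | Objectives, Aim 2 | Procedure | Analytical Plan |
|---|---|---|---|
| Task name | Alcohol Stroop | Stroop Color-Word Naming Task | Not named; alcohol and neutral words |
| Word classes | Not stated | Not stated (100 words) | Alcohol, neutral |
| Raw measures | Accuracy, reaction time | Error rate, reaction time | Error rate, reaction time |
| Contrast scored | Not stated | Not stated | Alcohol versus neutral (hypothesis only) |
| Model | Three-way, factors unnamed | None | Time and group |

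The raw measures agree across all three. The task name, the word classes, the derived score and the model term do not.

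**2. What the listed model tests**

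Let A and N be a participant's pre-to-post change in mean reaction time on alcohol and neutral words. With equal numbers of each, group x time on plain reaction time compares the groups on (A + N)/2. The hypothesis concerns A - N. If real stimulation changes both by the same amount d, the first quantity shifts by d and the second by d - d = 0.

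**3. Can the two scores disagree at this sample size?**

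The documents give no reaction-time SD or expected effect, so these inputs are assumptions: change SD 50 ms per word type, correlation between word types 0.5 to 0.9, t-tests on change, two-sided 0.05, 20,000 simulated trials. The 24 per group is from Sample Size.

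| Assumed effect of real stimulation | Significant, overall | Significant, alcohol minus neutral |
|---|---|---|
| Both word types 40 ms faster | 80-88% | about 5% |
| Alcohol 15 ms faster, neutral 15 ms slower | about 5% | 53-99% |
| Alcohol 30 ms faster, neutral 60 ms faster | 88-94% | 53-99.5%, in the unfavourable direction |

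**4. Precision of the two scores**

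Take trial SD s and assume the 100 words are split 50/50.

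- Trial-noise variance of the change in overall mean: 2s²/100.
- Trial-noise variance of the change in the difference: 2s²(1/50 + 1/50) = 8s²/100.
- Ratio: 4, whatever s is.

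With assumed s = 200 ms, the SDs are √800 = 28.3 ms and √3200 = 56.6 ms. For an assumed 30 ms group difference with 24 per group, power is 0.949 and 0.436.

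That counts trial noise only. If people also vary in how much their general speed changes, with SD g, then g² adds to the overall score and cancels from the difference. At s = 200, with no between-person variation in interference change, the variances are equal when 800 + g² = 3200, so g = √2400 = 49 ms. Overall-score power falls from 95% at g = 0 to 55% at g = 40 and 44% at g = 49. Beyond that the difference score is the more precise.

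The step 3 inputs say the same. The overall variance is 2500(1 + ρ)/2 and the difference variance is 5000(1 - ρ). They are equal at ρ = 0.6. At ρ = 0.9 the SDs are 49 ms and 22 ms.

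**The case against.** The strongest reply is that the three places can be read as one task told in parts: an alcohol Stroop in the aims, 100 words and colour naming in the procedure, alcohol and neutral words in the analysis. The procedural section opens with attentional bias towards alcohol cues, and its instruction to name the colour and ignore the meaning fits an alcohol Stroop. The colour-word sentence is a general remark about a well-known family of tasks. The three-way model in the aims may have word type as its third factor. The study is also a pilot, and Sample Size powers Aim 1 only.

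Much of this stands. A reader might infer that the plan states two rival endpoints, one of them overall reaction time. The documents do not support that: the procedural section never says the measures are scored overall, the aims contain no word-type score, and the raw measures match throughout. A reader might also infer that the hypothesis cannot be scored for anyone. That holds only if the list used has no alcohol words, and the word list of the downloaded task is not shown.

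The charitable reading still leaves a gap. It requires supplying word classes the procedure omits and a factor the Analytical Plan omits, and staff could follow the procedural text and run either task.

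**Conclusion.** The point holds as an inconsistency in task and score. The task has two names, the word classes are missing from the procedure, and the one stated hypothesis about word type sits beside a model that lacks word type. Taken as listed, the measures and model test general speed or accuracy rather than alcohol interference. This should be corrected before the data are analysed, and the task settled before first use.

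Its size cannot be stated as a property of this trial. The simulated and power figures show only that the two scores can give different, even opposite, answers with 24 per group; they rest on assumed SDs, correlations and effects. It is tempting to read the fourfold noise ratio as showing that the difference score is the weaker endpoint. The working does not support that: the ratio covers trial noise under a 50/50 split, and the ordering reverses once general-speed change varies enough between people.

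**What to change.** - **Procedure:** name the alcohol Stroop given in Objectives, Aim 2 as the task, and state that the 100 words include both alcohol words and matched neutral words, with the number of each.
- **Score:** define the Aim 2 primary score as the alcohol-minus-neutral difference in reaction time at each session, and likewise for error rate.
- **Test:** name the group x time x word-type interaction as the test of Aim 2; this is equivalent to group x time on the difference score. State it in both Objectives, Aim 2 and the Analytical Plan. It also reconciles the three-way model in the one with the two factors listed in the other.
- **Secondary:** report overall reaction time and overall error rate, so that a general change in speed is visible and is not taken for a change in interference.

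The cost is protocol wording and confirming that the tablet task loaded is the matching one. No extra visit, participant or testing time is needed. The drawback is that the difference score carries about four times the trial-noise variance under a 50/50 split. Because it also removes between-person variation in general speed change, its net precision may be lower or higher than that of overall reaction time.

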Hence, the goal of this proposal is to evaluate **Strategy 2 of the CNDS theory- increasing activity in executive control circuitry- as an innovative approach to dampening alcohol cue-reactivity (Aim 1) and improving cognitive control in the presence of an alcohol cue (Aim 2)**. This will be achieved through a double-blind, sham-controlled cohort study in 48 heavy alcohol drinkers with a history of alcohol-related injury. The brain reactivity to alcohol cues (Incentive Salience) and cognitive performance in the presence of an alcoholic beverage cue (Cognitive Control) will be measured immediately before and after participants receive real or sham intermittent theta burst stimulation (iTBS- a potentiating form of transcranial magnetic stimulation) to the dorsolateral prefrontal cortex (dLPFC iTBS). iTBS is a high-potency form of brain stimulation wherein two minutes of iTBS (600 pulses) leads to an increase in cortical excitability that lasts for approximately 30 minutes (Huang et al. 2005). In 2018, dLPFC iTBS was FDA-cleared as a treatment for major depressive disorder (wherein 30 sessions over 6 weeks lead to a sustained decrease in depressive symptoms for 6 months; Blumberger et al. 2018). In 2019, the first 2 manuscripts were published demonstrating that iTBS decreases cue-reactivity to cocaine (Steele et al 2019, Sanna et al 2019). **The goals of this pilot study are to quantify the acute effect of a single session of real or sham dLPFC iTBS on brain response to alcohol cues (Aim 1) and cognitive flexibility in the presence of an alcohol cue (Aim 2) among risky drinkers (“target engagement”)**.

Aim 1: Evaluate the effect of dLPFC iTBS on alcohol cue-reactivity. The blood-oxygen level dependent (BOLD) signal associated with exposure to alcohol cues will be measured before and after sham and real iTBS using a validated, patient-tailored alcohol/non-alcoholic beverage cue task. Hypothesis: cue-evoked functional connectivity in the dLPFC, ACC, amygdala, and ventral striatum will be attenuated after real but not sham iTBS.

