To determine the minimum number of participants necessary we performed a power calculation for the experiment based on our prior (Kearney-Ramos et al 2018). Based on the mean and standard deviation of mPFC activity in that study, Aim 1 will require 22 participants in both the real iTBS group and the sham iTBS group (95% power using two sided $p < 0.05$ level of significance). Assuming some loss of functional MRI data to movement artifacts (10%) we are proposing to enroll 48 participants (24 per group (real vs sham; 16 women (33%), 32 men (66%) based on prevalence of AUD in the US population. Integrity of the sham-control. The integrity of the blind will be assessed at the end of each visit with a standardized questionnaire regularly used in clinical trials of rTMS treatments. The randomization scheme for the study will be developed and monitored by a biostatistician associated with the Comprehensive Cancer Center's Biostatistical Shared Resource (to be named), and will be given to a member of the study team that has no contact with the participant. This person will set the MagVenture sham-controlled TMS system up before the PI, Co-I or research assistant enter the room with the patient. The data will be analyzed by the PI, Co-I and research assistant who will remain blinded until the end of the study.

Based on recruitment history from similar intervention studies in these individuals at Wake Forest Baptist hospital we anticipate that we will be able to recruit 3-4 participants per month (12-16 months = 48 participants). We have planned for 2 months of initial implementation and quality control assessment of the MRI scanning paradigm. Recruitment will commence in month 3 and likely continue through month 19. Data analysis (blinded) for Aim 1 (preprocessing, functional connectivity assessment) and Aim 2 (analysis of quality, rigor, and basic signal detection) will be ongoing. Months 20-24 will be spent performing final analyses, unblinding, preparing data for an R01 application and integrating outcomes with the clinical and preclinical projects within the WF-TARC in order to plan for future translational collaborations.

[figure not shown]
Interventions and Interactions

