Generalized Psychophysiological Interaction (gPPI): gPPI will be used to investigate task-modulated patterns of functional connectivity (FC) during the alcohol cue reactivity task. Regions-of-interest (ROIs) comprising frontal-striatal circuitry as well as elements of the Salience Network and Central Executive Network will be identified from the standard Automated Anatomical Labeling (AAL) Atlas. These included the vmPFC (AAL: left and right Frontal_Med_Orb), left caudate (AAL: Caudate_L), right caudate (AAL: Caudate_R), left putamen (AAL: Putamen_L), right putamen (AAL: Putamen_R), left insula (AAL: Insula_L), right insula (AAL: Insula_R), and anterior cingulate cortex (AAL: left and right Cingulum_Ant). These ROI masks will then be used in CONN Toolbox to extract ROI timecourses from

the fMRI data for subsequent gPPI computation. The Drug/Alcohol vs. Neutral contrast β s from the Pre- and Post-Real cTBS and Pre- and Post-Sham cTBS were entered into a two-way ANOVA and subsequent *t*-tests to determine the effect of treatment on changes in drug cue-evoked FC. More details on the analysis can be found in prior publications from our group (Kearney-Ramos et al 2018).

Results will be analyzed initially using descriptive statistics. Comparison between groups will be done using chi square tests for proportions, and *t*-tests or ANOVA procedures for continuous variables. Regression analysis will be performed to identify independent outcome predictors. Other inferential statistical analysis will be conducted as appropriate.

Relationship with the WF-TARC Goals:

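### The gPPI analysis names a mask for only one (ACC) of the four regions in the Aim 1 hypothesis, and none for the stimulated dLPFC or the amygdala

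*Combined protocol and SAP*

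**What the plan says.** Under Objectives, the Aim 1 hypothesis is that "cue-evoked functional connectivity in the dLPFC, ACC, amygdala, and ventral striatum will be attenuated after real but not sham iTBS". Under Methods and Measures, Design, the coil site is the left dLPFC at F3.

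Under Outcome Measure(s)/Analytical Plan, the gPPI paragraph says that regions from frontal-striatal circuitry and "elements of the Salience Network and Central Executive Network will be identified from the standard Automated Anatomical Labeling (AAL) Atlas". The list that follows opens "These included the vmPFC (AAL: left and right Frontal_Med_Orb), left caudate (AAL: Caudate_L), right caudate (AAL: Caudate_R), left putamen" and continues with the right putamen, left and right insula, and ACC. The next sentence makes the list the input to the analysis: "These ROI masks will then be used in CONN Toolbox to extract ROI timecourses from" the fMRI data. Alcohol-versus-neutral contrast betas then go into a two-way ANOVA with follow-up t-tests. For the rest, the reader is told that "More details on the analysis can be found in prior publications from our group".

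The section on the WF-TARC goals describes the dLPFC as a node of the Central Executive Network.

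**The concern.** The hypothesis and the analysis meant to test it name different regions. The dLPFC is the stimulated site, comes first in the hypothesis, and belongs to a network from which the gPPI paragraph promises elements. No dLPFC mask follows. The amygdala and the ventral striatum have none either.

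Two things are at stake. The first is interpretation: a change in vmPFC, caudate or insula connectivity would inform about cue-reactivity circuits but would not by itself confirm the written hypothesis. A null result there would not refute it. The second is prespecification. Sample Size describes Aim 1 connectivity work as continuing during recruitment, and Data and Safety Monitoring plans an efficacy analysis at 50% recruitment. Masks or connections not fixed in writing by then could be chosen after data have been seen.

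**Working it through.** The plan gives no figure of its own to reproduce on this point. The check compares two lists and then counts what the listed masks can reach.

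**Inputs.** Hypothesis regions (Objectives, Aim 1): 4. Listed masks (gPPI paragraph): 8, namely vmPFC, caudate left and right, putamen left and right, insula left and right, and ACC.

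**Step 1: match the lists.**

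| Hypothesis region | Mask named in the gPPI paragraph |
|---|---|
| dLPFC (stimulated, left) | none |
| ACC | yes |
| Amygdala | none |
| Ventral striatum | none by name; caudate and putamen are listed but not declared a proxy |

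So 1 of 4 regions has a named mask, or 2 of 4 with the proxy. Conversely, 8 − 1 = 7 of the 8 masks match no region named in the hypothesis. No other section names a mask for the missing three. The neuronavigation section compares the dLPFC target with individualized parcellation, but as a check on targeting.

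**Step 2: what the listed masks reach, if the list is complete.** The protocol does not say whether the analysis is ROI-to-ROI or seed-to-voxel, or whether connectivity in the four regions means any connection involving one of them or only connections among them. All four combinations are shown.

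- *ROI-to-ROI, any connection involving a region.* 8 × 7 / 2 = 28 pairs. ACC: 7. dLPFC: 0. Amygdala: 0. Ventral striatum: 0 by name. With the proxy, 28 − (4 × 3 / 2) = 22 pairs contain a caudate or putamen mask. Of these, 6 lie wholly inside the proxy, so 22 − 6 = 16 link it to another region.
- *Seed-to-voxel, any connection involving a region.* All 4 of 4 regions are reached, but the dLPFC and amygdala only as targets of other seeds.
- *ROI-to-ROI, connections among the four.* 4 × 3 / 2 = 6 pairs. Reached: 0, or 1 with the proxy (ACC with ventral striatum).
- *Seed-to-voxel, connections among the four.* Reached: 3 of 6 (ACC with each of the other three), or 5 of 6 with the proxy. The remaining pair is dLPFC with amygdala.

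**Step 3: how firm is 28?** It is one possible count. The eight entries cover ten AAL labels, since vmPFC and ACC each combine left and right; kept apart they give 10 × 9 / 2 = 45 pairs. If gPPI effects are kept directional, eight masks give 8 × 7 = 56. The number involving the dLPFC or the amygdala is zero in each case.

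**Step 4: if the list is open.** Further masks may be intended, but the protocol does not name them, so the counts in Step 2 do not apply and the masks are unspecified.

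**Step 5: the stated tests.** The two-way ANOVA and t-tests are described without saying which connections enter as the Aim 1 tests, and no multiplicity correction is given for them. The correction mentioned in the protocol belongs to the Aim 2 Stroop hypothesis.

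**The case against.** The best case for the plan has four parts.

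- The list can be read as illustrative, because it is introduced with the verb include after a sentence promising Central Executive Network elements. This stands as a possible reading. It changes the defect from omitted masks to unspecified ones, and the following sentence still treats the listed masks as the input.
- The hypothesis speaks of connectivity in the four regions, and a seed-to-voxel analysis from the listed masks would reach all four. This also stands, but the protocol does not say that the method is seed-to-voxel.
- The listed regions are reasonable. Design frames Aim 1 more broadly, as attenuating the limbic circuitry of cue-reactivity. The Background reports TMS effects in the caudate and cingulate. The sample size is drawn from mPFC data: "Based on the mean and standard deviation of mPFC activity in that study, Aim 1 will require 22 participants". They are sound regions to analyze, but they are not the four that the hypothesis names.
- Detail is deferred to earlier publications, and the analysts are blinded: "The data will be analyzed by the PI, Co-I and research assistant who will remain blinded until the end of the study". What those publications specify cannot be judged here, so the point is only that this protocol does not contain it. Blinding lowers the risk of data-driven choice without removing it; that risk is inferred.

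A reader might go further and infer that Aim 1 cannot be tested, or that dLPFC–amygdala connectivity is out of reach whatever is done. The documents support neither. The first overlooks the broader framing in Design. The second holds only if the list is closed, because an added dLPFC seed with a voxelwise search would reach the amygdala. A reader might also infer from the mention of cTBS and the past tense in the gPPI paragraph that the list was carried over from another study. The wording is consistent with that but does not establish it.

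**Conclusion.** The mismatch is real and should be fixed. As written, the gPPI paragraph does not directly test the regional hypothesis of Aim 1: 1 of 4 regions has a named mask, or 2 of 4 if caudate and putamen are declared the ventral-striatum proxy. The dLPFC and amygdala lack one either way.

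The consequence rests on what the protocol leaves open. With a complete list and ROI-to-ROI analysis, the dLPFC and amygdala predictions go untested. With seed-to-voxel, they are examined only from other seeds. With an open list, the masks are not prespecified. The finding is therefore an incompletely mapped hypothesis in a single-session target-engagement pilot, and it does not invalidate Aim 1. It uses no assumed effect size or power figure.

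**What to change.** Before the 50% analysis and before unblinding, reconcile the Aim 1 hypothesis with the gPPI paragraph in one of two ways:

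1. Add masks for the left dLPFC, the left and right amygdala and the ventral striatum, or declare caudate and putamen the ventral-striatum proxy. If the AAL atlas has no suitable label, name the mask source. Keep the existing masks as secondary.
2. Restate the Aim 1 hypothesis for the regions already listed. This also removes the contradiction, but leaves the stimulated site without a named mask.

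In either case, state in the protocol itself whether the analysis is ROI-to-ROI or seed-to-voxel. Name the connections that the two-way ANOVA and t-tests will treat as the Aim 1 tests, with a multiplicity correction. Which connections to choose is for the sponsor. The sample size rests on mPFC activity, so it gives no power basis for any particular connection.

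The cost is wording and up to four masks applied to scans already planned, with no new scans or participants. The downside is a few more tests to correct for, which a short named set keeps small.

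### Aim 1: adjusting post-TBS connectivity for its pre-TBS value would modestly sharpen the real-versus-sham comparison at no cost; Aim 2 needs one named test of its word-type hypothesis

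*Combined protocol and SAP*

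**What the plan says.** **Aim 1.** The Generalized Psychophysiological Interaction paragraph of Outcome Measure(s)/Analytical Plan takes the alcohol-versus-neutral contrast estimates of functional connectivity (FC). It says that those from "Pre- and Post-Real cTBS and Pre- and Post-Sham cTBS were entered into a two-way ANOVA", with t-tests to follow, "to determine the effect of treatment on changes in drug cue-evoked FC". No covariate is named. Further detail is left to outside papers: "More details on the analysis can be found in prior publications from our group". According to Objectives, the brain response is "measured immediately before and after participants receive real or sham" iTBS, so a pre-TBS value exists for each participant with usable scans. Sample Size states that "Aim 1 will require 22 participants in both the real iTBS group and the sham iTBS group", at 95% power and two-sided 0.05. It gives no mean difference, standard deviation or pre-post correlation.

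The Quality Assurance Plan under Data and Safety Monitoring says that baseline comparability between conditions will be inspected and analyses adjusted where needed.

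**Aim 2.** The Cognitive Interference paragraph of the Analytical Plan expects "slower color-naming responses for alcohol words compared to neutral words at baseline", with this effect smaller after real than after sham iTBS. The model in brackets is "mixed model analysis of variance, error rate and reaction time, before and after TBS, 2 groups: real iTBS and sham iTBS". Objectives, Aim 2, calls the task an alcohol Stroop and gives the model as "three way mixed model ANOVA, correcting for multiple comparisons", without naming the three factors. The task description under Interventions and Interactions presents a color-word Stroop with 100 words, makes error rates and reaction times primary, and does not mention word type.

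**The concern.** **Aim 1.** The natural reading of the two-way ANOVA is group (real, sham) by time (pre, post), with the interaction as the test. That uses the pre-TBS value as one level of time, which amounts to subtracting it in full. Unless pre and post values are very highly correlated, full subtraction adds noise that regression on the pre-TBS value would avoid. At stake is the width of the interval for the main real-versus-sham contrast in a small pilot whose estimates are to support a later grant application.

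**Aim 2.** The hypothesis concerns a difference between word types, but the factors listed beside it are only time and group. If the model were fitted to overall reaction time, it could not separate reduced alcohol interference from faster responding in general. Three sections describe the task or model differently, so two analysts could follow the plan and run different tests.

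**Working it through.** **Starting point in the plan.** The 22 per group cannot be reproduced, because no effect size or SD is given. Solving backwards (noncentral t, 22 per group, 95% power, two-sided 0.05, 42 df) gives a standardised difference d = 1.11. The plan does not say whether that is in units of the SD of change or of a single measurement.

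**Aim 1 formulas.** Let s be the SD of one measurement, equal before and after, and r the pre-post correlation.

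- Group by time (change score): variance proportional to 2s²(1 − r).
- ANCOVA: variance proportional to s²(1 − r²), times an allowance for chance baseline imbalance, 1 + t²/42 with t on 42 df. Its mean is 1 + (42/40)/42 = 1.025, or about 1.012 on the width.
- Ratio of widths: √((1 + r)/2) × 1.012 × (2.0195/2.0181). The last term is the price of the one degree of freedom (41 instead of 42).

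Example at r = 0.5: 0.866 × 1.012 × 1.001 = 0.877, so the interval is about 12% narrower.

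| Assumed r | √((1 + r)/2) | CI narrowing | ANCOVA power if d = 1.11 is in SDs of change (change score: 95%) | Change score / ANCOVA power if d = 1.11 is in single-measurement SDs |
|---|---|---|---|---|
| 0.3 | 0.806 | 18% | 99.3% | 86% / 96% |
| 0.5 | 0.866 | 12% | 98.4% | 95% / 98.4% |
| 0.7 | 0.922 | 7% | 97.1% | 99.6% / 99.9% |
| 0.9 | 0.975 | 1% | 95.4% | 100% / 100% |

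The gain vanishes at about r = 0.95 and becomes a loss of about 1% at r = 0.99. The smallest difference detectable with 80% power falls from 0.86 SD of change to 0.71, 0.76, 0.81 and 0.85 at the four values of r. Simulation with 40,000 runs per setting gave the same narrowing (0.183, 0.123, 0.067, 0.013).

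**Validity check.** In 20,000 simulated null trials per setting at r = 0.3, 0.5 and 0.7, the change-score test rejected in 5.1, 4.8 and 4.8% and ANCOVA in 5.0% each time. Both are valid.

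**Aim 2, sections side by side.**

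| Section | Task | Model or outcome |
|---|---|---|
| Objectives, Aim 2 | Alcohol Stroop | Three-way mixed ANOVA, factors unnamed; impairment at baseline without a stated comparator |
| Interventions and Interactions | Color-word Stroop, word type not mentioned | Error rates and reaction times primary |
| Analytical Plan | Alcohol versus neutral words | Mixed ANOVA; time and group listed |

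Suppose the words are half alcohol and half neutral, and that iTBS changes reaction time by D on alcohol words only. A time by group test on the overall mean then estimates D/2, whereas the word-type interaction estimates D. If iTBS instead speeds both types equally, the overall test responds although interference has not changed.

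An illustration with 24 per arm and 46 df: assume a general speed-up 0.3, 0.5 or 0.8 SD of change larger in the real arm. The noncentrality is d√(24/2), that is 1.04, 1.73 or 2.77. The overall test is then significant in 17, 40 or 77% of trials, while the alcohol-minus-neutral test stays near 5% (0.049 to 0.053 in 20,000 simulated runs, with interference independent of speed).

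**The case against.** The strongest reply on Aim 1 is that the plan already uses the baseline: pre-TBS FC is a level of time, the target is change, and the error rate is correct. That stands. A reader might infer that the plan ignores baseline, or that its test is biased; the documents support neither. A reader might also suspect that the four cells would be analysed as independent groups, since the text does not say repeated measures. The stated aim of testing effects on change makes that an unlikely reading.

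It can also be said that the Quality Assurance Plan already allows adjustment. It does, but only after baseline comparability has been inspected. It names neither the covariate nor the model, so it does not pre-specify this analysis. The cited earlier papers may say more, but they are not part of the plan.

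On Aim 2 the reply is stronger. The bracketed model can be read as time by group applied to the alcohol-versus-neutral effect just mentioned, which would be an appropriate test. The three-way ANOVA in Objectives fits word type by time by group. The task description is silent on alcohol words rather than contradictory. So the documents do not show that the contrast is missing from the analysis, or that no alcohol words will be presented. Moreover, Aim 2 is framed in Objectives as cognitive performance near an alcohol cue; under that wording a general improvement would itself be of interest. It misleads only as evidence for the interference hypothesis. What remains is that the factors are unnamed and three sections need to agree.

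**Conclusion.** **Aim 1, the main point, holds as a free improvement.** The planned test is valid but leaves some precision unused. The gain at 22 per arm is about 18% of CI width at r = 0.3, falling to 1% at r = 0.9 and to nothing near 0.95. It rests on an assumed r, equal variances before and after, and a linear relation. On the change-scale reading, power is already 95%, so conclusions would seldom differ. Nothing here shows that 22 per group or 48 in total is wrong.

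**Aim 2 is secondary and a matter of clarity.** The hypothesis, the listed factors and the task description should lead to one test, and at present they do not clearly do so. The 17, 40 and 77% are simply the power to detect an assumed general speed-up. No document suggests that one will occur, and they should not be read as an expected error rate.

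**What to change.** **Aim 1.** State that the decisive test is the real-versus-sham difference in post-TBS cue-evoked FC, adjusted for pre-TBS FC of the same measure (ANCOVA), with its 95% CI. Treat within-arm t-tests as descriptive. This settles the form of the test; the connection that is primary must still be named. While editing, reconcile the cTBS label in that paragraph with the iTBS named in Objectives, Sample Size and Interventions and Interactions. Cost: wording only, the same data, one degree of freedom, and a loss of about 1% in CI width if r is as high as 0.99.

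**Aim 2.** Align Objectives, the task description and the Analytical Plan. State that alcohol and neutral words are both shown and scored separately. Then name one test of the hypothesis for each of reaction time and errors: word type by time by group, or the between-group difference in the post-TBS alcohol-minus-neutral score adjusted for its pre-TBS value. Keep baseline slowing as a separate within-person comparison. Cost: wording only if the alcohol Stroop of Objectives is the task in use; otherwise the word list must be settled first.
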